7.14 Reporting of SAEs that are related and unexpected

An SAE form should be completed and faxed to the Chief Investigator within 24 hours. However, relapse, death and/or hospitalisations for elective treatment of a pre-existing condition do not need reporting as SAEs.

PROSTAGRAM	Protocol no: 18HH4595	Sponsor: Imperial College London	V 1.01MAY2019
-------------------	---------------------------------	---	----------------------

All SAEs should be reported to the relevant REC where in the opinion of the Chief Investigator, the event was:

- 'Related', i.e. resulted from the administration of any of the research procedures; and
 - 'Unexpected', i.e. an event that is not listed in the protocol as an expected occurrence
- Reports of related and unexpected SAEs should be submitted within 15 days of the Chief Investigator becoming aware of the event, using the NRES SAE form for non-IMP studies. The Chief Investigator must also notify the Sponsor of all SAEs. Local investigators should report any SAEs as required by their Local Research Ethics Committee, Sponsor and/or Research & Development Office.

Contact details for reporting SAEs are as follows:

Joint Research Compliance Office

Imperial College London and Imperial College Healthcare NHS Trust

E-mail: [contact]

Chief Investigator

[name] [name]

Imperial College London, Charing Cross Campus

E-mail: [contact]

[contact] (Mon to Fri 09.00 – 17.00)

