4.3 Exclusion criteria

1. Previous PSA test or prostate MRI within the prior two years of screening/consent visit
2. Evidence of a urinary tract infection or history of acute prostatitis within the last 6 months
3. Previous history of prostate cancer, prostate biopsy or treatment for prostate cancer (interventions for benign prostatic hyperplasia/bladder outflow obstruction is acceptable)
4. Any potential contraindication to MRI, including but not limited to:
 - a. Devices or metallic foreign bodies such as pacemakers, implantable defibrillators, neurostimulators, cochlear implants, coronary stents, prosthetic heart valves, aneurysm clips and other intravascular devices
 - b. Previous history of hip replacement surgery, metallic hip replacement or extensive pelvic orthopaedic metal
 - c. Claustrophobia
5. Any potential contraindication to prostate biopsy
6. Dementia or altered mental status that would prohibit the understanding or rendering of informed consent.
7. Any other medical condition precluding procedures described in the protocol

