7.3 Adverse Event recording

For the purposes of the study, AEs will be followed up according to local practice until the event has stabilised or resolved, or the Follow-up Visit, whichever is the sooner. Serious adverse Events (SAE) will be recorded throughout the study.

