7.6 Serious Adverse Events

7.6.1 Definition of SAE

An SAE is defined as any event that

- Results in death;
- Is life-threatening*;
- Requires hospitalisation or prolongation of existing inpatient's hospitalisation**;
- Results in persistent or significant disability or incapacity;
- Is a congenital abnormality or birth defect;

* "Life-threatening" in the definition of "serious" refers to an event in which the subject was at risk of death at the time of the event; it does not refer to an event which hypothetically might have caused death if it were more severe.

** "Hospitalisation" means any unexpected admission to a hospital department. It does not usually apply to scheduled admissions that were planned before study inclusion or visits to casualty (without admission).

Medical judgement should be exercised in deciding whether an adverse event/reaction is serious in other situations. Important adverse events/reactions that are not immediately life threatening, or do not result in death or hospitalisation but may jeopardise a subject, or may require intervention to prevent one of the other outcomes listed in the definition above should also be considered serious.

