7.11 Reporting of SAEs

Rapid reporting of all SAEs i.e. within 24 hours, occurring during the study must be performed as detailed in SAE reporting instructions. If the investigator becomes aware of safety information that appears to be related to the trial, involving a subject who participated in the study, even after an individual subject has completed the study, this should be reported to the Sponsor.

All SAEs will be reviewed by the Chief Investigator or a designated medically qualified representative to confirm expectedness and causality.

Reporting of SAEs and review by the CI will be via the trial data collection system (CRF/eCRF).

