## 10.4. Safety Variables

The frequency and incidence of adverse events (AEs) and serious adverse events (SAEs) occurring through the course of the study will be assessed.

An adverse event (AE) is any untoward medical occurrence in a patient or clinical trial subject. AEs will be recorded as any unfavourable and unintended sign or symptom, whether or not they are considered to be related to the trial protocol.

Serious adverse events (SAEs) will be recorded throughout the study. An SAE is defined as any event that

- Results in death;

Imperial Clinical Trials Unit	STATISTICAL ANALYSIS PLAN	PROSTAGRAM
-------------------------------	---------------------------	------------

- Is life threatening\*;
- Requires hospitalisation or prolongation of existing inpatient's hospitalisation\*\*;
- Results in persistent or significant disability or incapacity;
- Is a congenital abnormality or birth defect.

\* "Life-threatening" in the definition of "serious" refers to an event in which the subject was at risk of death at the time of the event; it does not refer to an event which hypothetically might have caused death if it were more severe.

\*\* "Hospitalisation" means any unexpected admission to a hospital department. It does not usually apply to scheduled admissions that were planned before study inclusion or visits to casualty (without admission).

Expected adverse events are listed in Appendix 3.

All protocol deviations and violations will be recorded throughout the study, and reported.

Imperial Clinical Trials Unit	STATISTICAL ANALYSIS PLAN	PROSTAGRAM
-------------------------------	---------------------------	------------

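### Protocol 7.14 exempts some or all deaths from SAE reporting, against the SAE definition in 7.6.1 and SAP 10.4 and the all-SAE rules in 7.11 and 7.14 itself

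*Protocol*

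**What the plan says.** The sentence at issue is in Protocol 7.14, directly after the instruction to fax an SAE form to the Chief Investigator within 24 hours: "However, relapse, death and/or hospitalisations for elective treatment of a pre-existing condition do not need reporting as SAEs". The same section later states: "The Chief Investigator must also notify the Sponsor of all SAEs".

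The other relevant provisions are:

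- **Definition.** Protocol 7.6.1 lists the criteria for an SAE, the first being "Results in death". SAP 10.4 repeats the list. In both, the only carve-out concerns hospitalisation: it means an unexpected admission, and does not usually cover admissions scheduled before inclusion or casualty visits without admission.
- **Reporting.** Protocol 7.11: "Rapid reporting of all SAEs i.e. within 24 hours, occurring during the study must be performed as detailed in SAE reporting instructions".
- **Review.** Protocol 7.11: "All SAEs will be reviewed by the Chief Investigator or a designated medically qualified representative to confirm expectedness and causality".
- **Recording.** Protocol 7.3: "Serious adverse Events (SAE) will be recorded throughout the study". SAP 10.4 says the same: "Serious adverse events (SAEs) will be recorded throughout the study".

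**The concern.** A definition with no exception for death, combined with rules that apply to all SAEs, means that every death during the study is reported and reviewed. The 7.14 sentence takes some or all deaths out of that reporting. A site that relied on it could, on the broad reading, leave a death after a study biopsy out of the 24-hour report and the expectedness and causality review.

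This matters in a study where men recruited from the community may be biopsied, a small proportion possibly under general anaesthetic. Protocol 7.10 lists death among the expected risks of the procedure under general anaesthetic. A death of that kind may therefore not count as unexpected under 7.13, and so may not trigger the 15-day report to the ethics committee in 7.14. The 24-hour report, the Chief Investigator's review and Sponsor notification would then be the remaining rapid routes, and these are the ones the sentence puts in doubt.

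**Working it through.** There is no arithmetic here. The check is whether any grammatical reading of the 7.14 sentence agrees with the rest of the two documents.

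**Two readings.** The qualifier about elective treatment of a pre-existing condition can attach to the last item only (broad reading) or to all three items (narrow reading).

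| Provision | Broad reading: every death exempt | Narrow reading: only deaths tied to elective treatment of a pre-existing condition exempt |
|---|---|---|
| 7.6.1 and SAP 10.4: an event resulting in death is an SAE | Conflicts for all deaths | Conflicts for that subset, which still meets the criterion |
| 7.11: all SAEs reported within 24 hours | Conflicts, because each death is an SAE | Conflicts for that subset |
| 7.11: all SAEs reviewed for expectedness and causality | Conflicts | Conflicts for that subset |
| 7.14: Sponsor notified of all SAEs | Conflicts within one section | Conflicts for that subset |
| 7.3 and SAP 10.4: SAEs recorded throughout | Recording is still required | Recording is still required |

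**Item by item.**

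- *Death* carries the conflict on both readings.
- *Hospitalisation* for elective treatment is broadly compatible with the unexpected-admission note in 7.6.1.
- *Relapse* is not an SAE criterion. It conflicts only where a relapse also meets one. The protocol does not define it, and 4.3 excludes men with "Previous history of prostate cancer, prostate biopsy or treatment for prostate cancer", so it has no clear referent for the target disease.

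**Count of provisions.** Two passages make an event that results in death an SAE (7.6.1 and its copy in SAP 10.4). Three sentences set unconditional rules for all SAEs (two in 7.11, one in 7.14). These do not name death themselves; they reach it through the definition. Two sentences require SAEs to be recorded throughout (7.3 and SAP 10.4). Apart from the 7.14 sentence, no passage in either document states an exception for death.

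**The case against.** The strongest reply is that 7.14 exempts events from reporting and does not redefine them. An event can be defined and recorded as an SAE yet be excused from one reporting route. Because the sentence follows the instruction on the faxed form, it might excuse only that form, while 7.11 still routes reporting and review through the CRF/eCRF. Other safeguards remain: adverse events are reconciled on the eCRF at the final visit (SAP 11.3 and 14), annual reports list all recorded SAEs (Protocol 7.15 and 10.5), and SAP Tables 1.5.7 and 1.5.8 have a category for death. The SAE reporting instructions named in 7.11 are not in these documents and may be clear.

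Part of this stands. The direct clash is over reporting and review. SAP 10.4 governs definition and recording, not expedited reporting, and because recording is required separately, a death need not vanish from the SAP tables.

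The rest does not remove the conflict. The wording of the exemption is general and is not confined to a fax. The eCRF is the route for the same SAE reports that 7.14 says are not needed. Limiting the exemption to 7.14 still leaves that section at odds with its own Sponsor rule. Separate instructions cannot cure contradictory protocol text. The narrow reading is the milder one, and under it a death after a study biopsy is not exempt, but nothing in the protocol rules out the broad reading.

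**Conclusion.** The contradiction is real on either reading, and the passages must be reconciled. On the broad reading the exemption covers all deaths; on the narrow reading it covers only deaths tied to elective treatment of a pre-existing condition. No number of affected events is claimed, and the primary estimate is untouched. Loss of a death from the SAP's SAE tables is possible but does not follow automatically. The conclusion rests on the text of the two documents alone. It should be fixed because it concerns the reporting of the most serious safety outcome and the correction is small.

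**What to change.** Amend the 7.14 sentence by striking *relapse*, *death* and the joining *and/or*, so that hospitalisations for elective treatment of a pre-existing condition are the only exempt item. Deaths then follow the existing 24-hour reporting and review rule in 7.11, and no new rule is introduced. *Relapse* can go at the same time, since the protocol does not define it.

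No other section has to change to remove the conflict over death. Two looser points would remain and could be tidied in the same amendment: elective admissions arranged after inclusion, which the 7.6.1 note does not clearly cover, and the faxed form in 7.14 beside the CRF/eCRF route in 7.11.

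The cost is a one-line wording amendment, with no change to the sample size, the data collected or the analysis.

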7.15 Annual reporting of Serious Adverse Events

Annual Progress reports will be submitted to the Research Ethics Committee and the Sponsor in accordance with local requirements. The annual Progress report will detail all SAE recorded.

7.16 Reporting urgent safety measures

If any urgent safety measures are taken the CI/Sponsor shall immediately and in any event no later than 3 days from the date the measures are taken, give written notice to the relevant REC of the measures taken and the circumstances giving rise to those measures.

8. DISCONTINUATION & WITHDRAWAL FROM STUDY

8.1 Study Discontinuation by the sponsor

The Sponsor may terminate the study at any time if the following occur, and the investigator is unable to take corrective action in any of these cases:

- The investigator is non-compliant with the protocol
- The investigator is non-compliant with the regulatory requirements

PROSTAGRAM	Protocol no: 18HH4595	Sponsor: Imperial College London	V 1.01MAY2019
-------------------	---------------------------------	---	----------------------

- The investigator is non-compliant with the principles of Good Clinical Practice as outlined in the Declaration of Helsinki and the Research Governance Framework
- The CRF completion is inadequate

8.2 Study Discontinuation by the Chief Investigator

If an unwanted effect is considered severe by the Chief Investigator and endangers the health of all patients, the study will be discontinued after agreement with the Sponsor.

8.3 Study Discontinuation for an individual patient

The criteria for discontinuing the study in the case on individual patients are:

- Intercurrent illness: Any illness, which in the judgment of the investigators would affect the assessments of clinical status to a significant degree
- Request by the patient: It is the patients right to request discontinuation of their participation in the study. If this request is made, it will be respected and will not affect the patient's ability to receive medical care from the investigators now or in the future.
- Discontinuation of attendance at the investigating site: Efforts should be made to maintain the investigations schedule and continue follow-up, even if patients no longer attend the participating institution.

8.4 Withdrawal from Study

Withdrawal from the study refers to discontinuation of study intervention and study procedures and can occur for the following reasons:

- Participant decision
- Inability to conduct any one of the imaging tests, blood tests or biopsies according to protocol.
- Loss to follow-up

8.4.1 Procedures for Withdrawal from Study

Each participant has the right to withdraw from the study at any time. Withdrawal may be complete (i.e. from further study procedures and any follow up), or partial (e.g. from study procedures but allowing the possibility of further follow up). All communication surrounding the withdrawal should be noted in the patient's records, and where withdrawal is complete, no further CRFs should be completed for that patient. Data up to the time of withdrawal can be included in the study if anonymised.

Participants who withdraw will be replaced to maintain the accrual of patients.

All participants who withdraw will remain eligible for follow-up via standard of care prostate cancer screening which is available through informed discussion of the risks and benefits with their GP.

PROSTAGRAM	Protocol no: 18HH4595	Sponsor: Imperial College London	V 1.01MAY2019
------------	--------------------------	-------------------------------------	---------------

9. STATISTICAL ANALYSES

9.1 Sample Size and power considerations

The study is powered for the primary objective to determine the prevalence of screen-positive MRIs in the general male population aged 50-69 years. We have followed the formula recommended by Naing et al(46) to determine an adequate sample size to estimate the prevalence of screen positive MRIs with a precision of +/- 5%

$$n = \frac{Z^2 P(1-P)}{d^2}$$

Z = Z statistics for a level of confidence

P = expected prevalence or proportion

d = precision.

The sample size calculation requires an estimate of the prevalence of screen-positive MRI (p). There are no previous studies that provide a reliable estimate of this figure in 50-69 years at average risk of prostate cancer. We have estimated this figure based on a number of assumptions, which are listed below. We have split the population into 2 groups depending on PSA level, as there are different levels of evidence for each group.

GROUP 1: PSA raised (PSA ≥ 3.0):

We have assumed this to be 73% based on a combination of studies.

- The PROMIS study has shown that in a group of biopsy-naïve men referred with a suspicion of prostate cancer, the prevalence of positive MRI (Likert ≥ 3) was 72.6%(7).
- The PRECISION study which used PI-RADS v2 and found a prevalence of 71.1% (47) for PIRADS ≥ 3.
- A recent review, which did not include PROMIS and PRECISION, categorising PI-RADS threshold across different groups of men confirmed that 73% of biopsy-naïve men have a positive scan defined as PI-RADS score(48).

GROUP 2: PSA normal (PSA ≤ 3.0):

There is limited data on the number of positive MRIs in this group so we have combined previous research estimating

1. The prevalence of expected significant cancers
2. The performance characteristics of MRI:

1. The prevalence of clinically significant disease in men with normal PSA

In the Prostate Cancer Prevention Trial (PCPT), this estimated that the prevalence of clinically significant disease in a normal PSA population is 2.20% (49, 50). The reference test was a 6-core (sextant) biopsy, which is known to underestimate the presence of cancer

PROSTAGRAM	Protocol no: 18HH4595	Sponsor: Imperial College London	V 1.01MAY2019
-------------------	---------------------------------	---	----------------------

and has been replaced with a 10-12 core approach. However, we do not have any reference to estimate by how much the 6-core biopsy underestimates the clinically significant disease in a normal PSA population. Therefore, we hypothesise that the prevalence of undiagnosed clinically significant disease in this group is 2.20%.

2. The performance characteristics of MRI:

- a. We will assume that the performance characteristics (sensitivity and specificity) of mp-MRI to detect clinically significant disease are the same in a normal and raised PSA population.
- b. These performance characteristics are variable across the literature.
 - i. A meta-analysis by Rooij et al 2014(51) reported a sensitivity and specificity of 74% and 88% respectively.
 - ii. The recent PROMIS study(7) (not included in Rooij et al) reported a sensitivity and specificity of 93% and 41% respectively.
- c. We have calculated the assumed prevalence of a positive MRI in a normal PSA population using both these performance characteristics using the following 2x2 table.

		Clinically significant prostate cancer		
		Diseased	Non-diseased	Total
MRI	Positive	a	b	P Normal PSA
	Negative	c	d	
	Total	2.20%	97.80%	

d. Based on the performance characteristics in Rooij et al 2014:

- i. Sensitivity: 74%

$$a / (a+c) = 0.74$$

$$a / 0.022 = 0.74$$

$$a = 0.0163 \quad c = 0.0057$$

- ii. Specificity: 88%

$$d / (b+d) = 0.88$$

$$d / 0.978 = 0.88$$

$$b = 0.1174 \quad d = 0.8606$$

PROSTAGRAM	Protocol no: 18HH4595	Sponsor: Imperial College London	V 1.01MAY2019
-------------------	---------------------------------	---	----------------------

ROOIJ ET AL 2014		Clinically significant prostate cancer		
MRI		Diseased	Non- diseased	Total
	Positive	1.63%	11.74%	13.37%
	Negative	0.57%	86.06%	86.63%
	Total	2.20%	97.80%	

Based on the performance characteristics in [name] et al 2017:

iii. Sensitivity: 93%

$$a/(a+c) = 0.93$$

$$a/0.022 = 0.93$$

$$a = 0.0205 \quad c = 0.0015$$

iv. Specificity: 41%

$$d/(b+d) = 0.41$$

$$d/0.978 = 0.41$$

$$b = 0.5770 \quad d = 0.4010$$

AHMED AL 2017		Clinically significant prostate cancer		
MRI		Diseased	Non- diseased	Total
	Positive	2.05%	57.70%	59.75%
	Negative	0.15%	40.10%	40.25%
	Total	2.20%	97.80%	

- e. Therefore given these performance characteristics the prevalence of a positive MRI in a normal PSA population will be either
- i. 13.37% based on Rooij et al 2014(51)
 - ii. 59.75% based on [name] et al 2017 (7).

[figure not shown]
PROSTAGRAM	Protocol no: 18HH4595	Sponsor: Imperial College London	V 1.01MAY2019
-------------------	---------------------------------	---	----------------------

The final part of the calculation is to combine the assumed prevalence of positive MRI in the normal and raised PSA groups to estimate the prevalence of positive MRI in a mixed population. There is high quality evidence for the expected percentage of normal and raised PSA from the Cluster randomised trial of PSA testing for Prostate cancer (CAP)(52), namely:-

- Raised PSA: 10.4%
- Normal PSA: 89.6%.

Therefore, using our estimates above for the prevalence of positive MRIs in a normal PSA population, we expect 11.98% (13.37% of 89.6%) (Rooij et al) and 53.54% (59.75% of 89.6%) ([name] et al). The positive prevalence in a raised PSA population is 7.59% (73% of 10.4%).

This produces an assumed prevalence of positive MRI in both groups of 19.6% (Rooij et al) or 61.1% ([name] et al). Based on 95% confidence interval ($z = 1.96$) and precision (d) 0.05, these sample sizes can be represented on the below graph at different prevalence estimates.

Using the formula by Naing et al. (46), assuming a prevalence of 19.6% requires a sample size of 243 participants. While assuming a prevalence of 61.1% will require a sample size of 366 participants. Allowing for a 10% dropout this requires a sample size of 270 and 406 participants respectively.

PROSTAGRAM	Protocol no: 18HH4595	Sponsor: Imperial College London	V 1.01MAY2019
-------------------	---------------------------------	---	----------------------

9.2 Recruitment rates

The estimated postal response rate is 10-20% based on the experience of the CAP study. Given an expected 10% response rate, we will need to post 4,800 letters to reach recruitment targets with postal recruitment alone. It is unknown the recruitment rates for opportunistic and other forms of recruitment. The recruitment rates will be monitored to ensure a stable recruitment rate given MRI and biopsy capacity.

9.3 Data Analysis

A statistical analysis plan will be prepared and finalised prior to database lock.

PROSTAGRAM	Protocol no: 18HH4595	Sponsor: Imperial College London	V 1.01MAY2019
------------	--------------------------	-------------------------------------	---------------

